8.3 Reasons for Removal From Treatment or Study

8.3.1 Reasons for Removal From Treatment

Reasons for removal from protocol-required investigational product(s) or procedural assessments include any of the following:

- subject request
- safety concern (eg, due to an adverse event, ineligibility determined, protocol deviation, non-compliance, requirement for alternative therapy)
- death
- lost to follow-up
- decision by sponsor (other than subject request, safety concern, lost to follow-up)

- other protocol-specified criteria:
 - o pregnancy
 - anaphylactic reaction likely related to IP
 - o bone adverse event likely related to IP (eg, atypical femoral fracture)
 - neurologic adverse event likely related to IP (eg, facial cranial nerve-related signs or symptoms)
 - o disease flare or medical event requiring treatment not allowed in the protocol
 - o severe or symptomatic hypocalcemia
 - Subjects who are removed from treatment as a result of severe or symptomatic hypocalcemia should receive treatment according to local standard of care, at the discretion of the treatment physician and should be closely followed up until resolution of the adverse event.
 - o ONJ
 - o dental abnormality requiring invasive dental procedures

8.3.2 Reasons for Removal From Study

Reasons for removal of a subject from the study are:

- decision by sponsor
- withdrawal of consent from study
- death
- lost to follow-up

9. SAFETY DATA COLLECTION, RECORDING, AND REPORTING

9.1 Definition of Safety Events

9.1.1 Adverse Events

An adverse event is defined as any untoward medical occurrence in a clinical trial subject. The event does not necessarily have a causal relationship with study treatment. The investigator is responsible for ensuring that any adverse events observed by the investigator or reported by the subject after signing of the ICF through day 169/EOS visit, End of Treatment visit, or 30 days after the last dose of IP (whichever period is longer) are reported using the Events eCRF.

The definition of adverse events includes worsening of a pre-existing medical condition. Worsening indicates that the pre-existing medical condition or underlying disease (eg, diabetes, migraine headaches, and gout) has increased in severity, frequency, and/or duration more than would be expected and/or has an association with a significantly worse outcome than expected. A pre-existing condition that has not worsened more than anticipated (ie, more than usual fluctuation of disease) during the study, or involves an intervention such as elective cosmetic surgery or a medical

procedure while on study, is not considered an adverse event. Change in severity from previously reported grade to another distinct grade (in the opinion of the investigator) should be recorded on the Event eCRF. The investigator's clinical judgment is used to determine whether a subject is to be removed from treatment due to an adverse event. In the event a subject, or subject's legally acceptable representative requests to withdraw from protocol-required therapies or the study due to an adverse event, refer to Section 8.1 for additional instructions on the procedures recommended for safe withdrawal from protocol-required therapies or the study.

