2. BACKGROUND AND RATIONALE

2.1 Disease

Osteogenesis imperfecta is a group of genetic skeletal disorders characterized by increased bone fragility, low bone mass (Rauch and Glorieux, 2004), and increased bone turnover (Rauch et al, 2009) contributing to osteoporosis, fractures, and other conditions. OI is the most common form of primary osteoporosis in children with an estimated incidence of 1 per 25,000 live births (Byers, 2000; Mäkitie, 2013).

At least twelve types of OI have been identified based on clinical phenotype and underlying genetic defect (Marini and Blissett, 2013). The majority of individuals with OI are heterozygous for mutations in the type I collagen genes (collagen type I alpha 1 [COL1A1] or collagen type I alpha 2 [COL1A2]) that lead to quantitative and/or qualitative defects in collagen synthesis and negatively impact bone strength (van Dijk et al, 2012).

The clinical features of OI may include fractures, short stature, hyperlaxity of ligaments and skin, hearing loss, blue sclera, and dentinogenesis imperfecta (Steiner et al, 2005). The clinical severity of OI caused by dominantly inherited collagen mutations varies from mild, non-deforming to perinatal lethal; most children with OI experience recurrent fractures, with or without progressive deformity, disability, and pain (Rauch and Glorieux, 2004; Cheung and Glorieux, 2008). The most common OI presentation are listed below:

- Type I: the mildest form; no skeletal deformity; may have fractures with ambulation; vertebral scoliosis may also occur.
- Type II: the most severe form; multiple fractures and skeletal deformity in utero; usually fatal in the neonatal period.

- Type III: next-most-severe form after type II; severe skeletal deformities and bone fragility from a young age; fractures may occur from the in utero period through adulthood; scoliosis may be severe.
- Type IV: variable mild to severe; moderate skeletal deformity.
- Type V: moderate skeletal deformity and moderate-to-severe bone fragility, with hypertrophic callus formation after some fractures, intraosseous membrane calcification, congenital dislocation of the radial head.

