2.3 Pediatric Risk Assessment

Romosozumab has demonstrated a favorable benefit-risk in postmenopausal women at high risk for fracture. The safety profile was evaluated in more than 14,000 subjects with the most common adverse reactions (\geq 1/10) being viral upper respiratory tract infection and arthralgia. Key safety risks for romosozumab include serious cardiovascular events of myocardial infarction and stroke, hypersensitivity reactions, hypocalcemia, and rare cases of osteonecrosis of the jaw (ONJ) and atypical femoral fracture (AFF). More detailed information about the known and expected benefits and risks may be found in the Romosozumab Investigator's Brochure.

Overall, pediatric subjects treated with romosozumab in this study are expected to have a risk profile comparable to that observed in adults. The potential risk of serious

cardiovascular adverse events of myocardial infarction and stroke is however not anticipated to occur in pediatric patients as such events are not typically observed in pediatric populations. Nonetheless subjects will be closely monitored and those at a high risk of cardiovascular disease (eg, familial hypercholesterolemia, valvular heart disease, or Kawasaki disease) will be excluded from this study.

Events of interest specific to the pediatric patient population include cranial hyperostosis and the effect on longitudinal bone growth, as well as effects on fetal development in those female subjects with reproductive potential, and are further discussed below.

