9.4 Demographic and Baseline Characteristics

Demographic (ie, collected age (years), sex, race, ethnicity (Hispanic, non-Hispanic), body composition (height [cm], weight [kg], BMI [kg/m²])) and baseline disease

characteristics (ie, lumbar spine BMD, bone mineral content (BMC), bone area, and BMD Z-score, bone turnover markers (sCTX, P1NP), laboratory parameters (calcium corrected by albumin, phosphorus, creatinine, serum 25-OH vitamin D, eGFR), iPTH, fracture history (Any historical fracture (Yes, No), **nonvertebral fracture**), baseline use of vitamin D, baseline use of calcium, prior osteoporosis medication use (Yes, No), type of OI (I, II, III, and IV) will be summarized by cohort using descriptive statistics based on the Full Analysis Set defined in Section **6.1**.

Historical nonvertebral fractures are as reported on fracture history eCRF, excluding skull, facial, mandible, cervical vertebrae, thoracic vertebrae, lumbar vertebrae, metacarpus, finger phalanges, and toe phalanges and fractures associated with high trauma or pathologic fractures.

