9.6 Safety Analyses

9.6.1 Adverse Event

The Medical Dictionary for Regulatory Activities (MedDRA) version 25.0 or later will be used to code all events categorized as adverse events to a system organ class and a preferred term.

The subject incidence of adverse events will be summarized for all treatmentemergent adverse events, serious adverse events, adverse events leading to withdrawal of

investigational product, fatal adverse events, and adverse events of interest. The severity grade of all treatment-emergent

adverse events will be summarized based on Severity Intensity Scale for Adverse Events.

Subject incidence of all treatment-emergent adverse events, serious adverse events, adverse events leading to withdrawal of investigational product, and fatal adverse events will be tabulated by system organ class and preferred term in descending order of frequency. Subject listing of all treatment-emergent adverse events will also be provided.

Subject incidence of events of interest (EOI; standardized MedDRA queries and/or Amgen customized queries) will also be summarized according to their categories and preferred term. Events of interest of hypersensitivity and malignancy will be identified using a narrow search/scope in standardized MedDRA queries (SMQ). Event of interest of hypocalcemia, injection site reaction, hyperostosis and osteoarthritis will be identified using Amgen-defined MedDRA search strategies. **Serious cardiovascular adverse events will be identified using cardiac and vascular system organ class (SOC) in MedDRA.** Adjudicated-positive adverse events of osteonecrosis of the jaw (ONJ) will also be summarized as EOIs.

The number and percentage of subjects reporting adverse events will be evaluated for each dose cohort, across dose cohorts, and will also be tabulated by relationship to study drug. In addition, summary of cranial nerve examination at each visit and the result change from entry exam over time for each cohort will be tabulated.

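### Protocol 9.1.1 leaves it to each site whether a new fracture in a child with OI is an adverse event, and no event of interest covers fracture

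*Protocol*

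**What the plan says.** Protocol Section 9.1.1 opens broadly: "An adverse event is defined as any untoward medical occurrence in a clinical trial subject", whatever the cause. It then treats pre-existing illness separately. Such an illness counts as worsened only if it "has increased in severity, frequency, and/or duration more than would be expected", or has a clearly worse outcome than expected. The section excludes from adverse events "A pre-existing condition that has not worsened more than anticipated (ie, more than usual fluctuation of disease) during the study".

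Section 2.1 states that "most children with OI experience recurrent fractures". Section 9.1.2 defines a serious adverse event as an adverse event that meets a serious criterion.

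Fracture history is taken up to enrolment (Section 7.4.4) and summarised as a baseline characteristic in SAP 9.4, where "Historical nonvertebral fractures are as reported on fracture history eCRF".

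On events of interest, Protocol 10.4.3.7 gives examples that include neither fracture nor atypical femoral fracture (AFF). SAP 9.6.1 goes category by category. Hypersensitivity and malignancy come from standardised queries, and serious cardiovascular events from system organ classes. Then: "Event of interest of hypocalcemia, injection site reaction, hyperostosis and osteoarthritis will be identified using Amgen-defined MedDRA search strategies". Adjudicated osteonecrosis of the jaw (ONJ) completes the list.

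**The concern.** Every subject enters with OI as the underlying disease, and fracture is how that disease usually shows itself. A rule that excludes ordinary disease activity, judged partly by frequency, gives a site a textual reason not to record a fracture in a child who has always fractured. Another site, relying on the general definition, would record the same event.

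At stake is the completeness of the fracture safety data for a bone-acting antibody in a bone-fragility population. If recording varies by site, the adverse event tables cannot separate a difference between cohorts from a difference in site practice, because an event never entered cannot be recovered in the analysis.

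The event-of-interest gap is a second, smaller matter. The plan names a femoral fracture type as a key risk but provides no summary that would bring fractures, or femoral fractures, together by cohort.

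**Working it through.** The documents state no figure on this point, so the check is mainly a comparison of texts.

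1. **Does a new fracture fit the general definition?** Yes. It is an untoward occurrence. Exclusion criterion 210 keeps out children with an unhealed fracture, so a break on study is new.

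2. **Can it also fall under the exclusion?** Yes. OI is pre-existing in every subject. Section 9.1.1 illustrates underlying disease with migraine and gout among its examples. Both come in discrete episodes, so the rule is not confined to steady states. A child who breaks a bone about as often as before has not worsened in frequency. No expected fracture frequency is given against which a site could judge.

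3. **Does another section settle it?** No. Sections 7.4.17.1, 9.2.1 and 10.4.3.7 do not say that a new fracture must be recorded.

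4. **Is there another on-study record?** None is dedicated to fractures. They are not among the endpoints (10.1.1), and fracture history stops at enrolment. Concomitant treatments are recorded with their indication (6.5, 7.4.16), and physical examinations are repeated (7.3). These could hint at a fracture but yield no fracture count.

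5. **Does the ambiguity reach serious events?** Yes, because 9.1.2 builds the serious event on the adverse event.

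6. **How much does one child matter?** Each cohort has 4 subjects (Table 2). Recording or omitting one child's only fracture changes the cohort's subject incidence by 1/4 = 25 percentage points. Across all cohorts the change is 1/16 = 6.25 points, or 1/24 = 4.2 points if the optional cohorts enrol.

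7. **ONJ and AFF side by side:**

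| Place | ONJ | AFF |
|---|---|---|
| Protocol 2.3, key risks | named | named |
| Protocol 7.4.17.1, adjudication | yes | no |
| Protocol 8.3.1, removal from treatment | named | named as example |
| Protocol 10.4.3.7, examples of interest | not named | not named |
| SAP 9.6.1, events of interest | yes | no |

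The two risks start level in 2.3, and only one has a dedicated summary in the SAP.

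**The case against.** The strongest reply is that 9.1.1 excludes a condition, not events. OI is the condition and a new break is a new occurrence, so the general definition applies. Other text points the same way. Section 8.3.1 itself treats AFF as a bone adverse event. Section 9.1.2 says that no serious events are exempt from individual expedited reporting, and it offers emergency visits and urgent intervention as examples of medically important events. The summary of changes for Amendment 1 records that a separate disease-related-event category was removed, which suggests that fractures were meant to go through ordinary reporting. All of this stands as evidence of intent. None of it tells a site how to apply the frequency test to a child with recurrent fractures.

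On events of interest, the protocol list is only illustrative, and any recorded fracture would appear in the preferred-term tables and the subject listing under SAP 9.6.1. That also stands: a recorded AFF would not be invisible. The Amendment 1 summary explains why AFF adjudication was dropped: femoral fractures are common in OI and cannot be told apart radiographically from AFF. That is a fair reason not to adjudicate. It does not explain the absence of any femoral-fracture summary, which needs no such distinction.

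A reader might infer more than the documents support:

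- **That fractures are excluded outright, or that serious fractures will go unreported.** The text permits either reading and requires neither.
- **That the removal criterion or the dose stopping rules would fail.** The bone-event criterion in 8.3.1 covers events likely related to treatment, and Table 3 acts on suspected drug reactions. A fracture judged to be such would hardly be classed as ordinary OI, so these rules are little affected.
- **That a stated number of fractures will be lost.** Follow-up is about 169 days for 16 to 24 subjects, which is 16 × 169/365.25 = 7.4 to 24 × 169/365.25 = 11.1 child-years. The documents give neither a fracture rate nor a rate of non-recording to apply to it.

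**Conclusion.** The concern holds as an ambiguity in a recording rule. Section 9.1.1 supports two opposite classifications of the same new fracture, nothing else in the plan decides between them, and no dedicated record would catch a fracture left out. Serious-event status depends on the same choice. The demonstrable size is the weight of one child: 25 percentage points of incidence in a cohort of 4. How many fractures would be affected cannot be estimated from the documents. The conclusion assumes that at least some investigators would apply the exclusion to OI fractures, which the wording and Section 2.1 allow but do not prove.

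The missing fracture event of interest is a real but lesser gap, because recorded fractures would still appear in the general tables. Both should be corrected.

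**What to change.** In Protocol 9.1.1 and 9.2.1, state that every new fracture in the adverse event reporting period is recorded as an adverse event, whatever the child's previous fracture frequency, and is assessed for seriousness in the usual way. The period should run from consent, as those two sections already specify. Section 5 (from enrolment) and Section 7.4.17.1 (after first dose) give later starting points and should be aligned.

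In Protocol 10.4.3.7 and SAP 9.6.1, add fracture as an event of interest by cohort, with femoral fracture as a subset. Limit it to treatment-emergent events as defined in SAP 5.1, and show it beside baseline fracture history. The any-fracture item in SAP 9.4 is the closer companion, because the nonvertebral item leaves out several sites and high-trauma fractures. History covers a different length of time, so it gives context and is not a comparator. AFF adjudication need not return.

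The change affects recording and summary only. It takes a sentence in each protocol section and one event-of-interest category with its search terms. A trauma-level field would help interpretation but should be optional, since it is not among the attributes in 9.2.1 and may need a case report form change. The drawback is that adverse event counts will rise because ordinary OI fractures are counted.

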9.1.2 Serious Adverse Events

A serious adverse event is defined as an adverse event that meets at least 1 of the following serious criteria:

- fatal
- life threatening (places the subject at immediate risk of death)
- requires in patient hospitalization or prolongation of existing hospitalization
- results in persistent or significant disability/incapacity
- congenital anomaly/birth defect
- other medically important serious event

There are no anticipated serious adverse events that are not planned to be reported individually in an expedited manner.

An adverse event would meet the criterion of "requires hospitalization", if the event necessitated an admission to a health care facility (eg, overnight stay).

If an investigator considers an event to be clinically important, but it does not meet any of the serious criteria, the event could be classified as a serious adverse event under the criterion of "other medically important serious event". Examples of such events could include allergic bronchospasm, convulsions, blood dyscrasias, drug induced liver injury (DILI) (see Appendix A for DILI reporting criteria), or events that necessitate an emergency room visit, outpatient surgery, or urgent intervention.

9.2 Safety Event Reporting Procedures

9.2.1 Reporting Procedures for Adverse Events That do not Meet Serious Criteria

The investigator is responsible for ensuring that all adverse events observed by the investigator or reported by the subject that occur after signing of the ICF through day 169/EOS visit, ET visit, or 30 days after the last dose of IP (whichever period is

longer) are reported using the Events eCRF. The investigator must assign the following adverse event attributes:

- Adverse event diagnosis or syndrome(s), if known (if not known, signs or symptoms),
- Dates of onset and resolution (if resolved),
- Did the event start prior to first dose of investigational product, other protocol-required therapies,
- Assessment of seriousness,
- Severity,
- Assessment of relatedness to IP (romosozumab), other protocol-required therapies, and/or study-mandated activity and/or procedures;
- Action taken, and
- Outcome of event

The adverse event grading scale used will be the **Severity Intensity** Scale **for Adverse Events**. The grading scale used in this study is described in Appendix A.

The investigator must assess whether the adverse event is possibly related to the investigational product. This relationship is indicated by a "yes" or "no" response to the question: "Is there a reasonable possibility that the event may have been caused by the investigational product?" Relatedness means that there are facts or reasons to support a relationship between investigational product and the event.

The investigator must assess whether the adverse event is possibly related to other protocol-required therapies. This relationship is indicated by a "yes" or "no" response to the question: Is there a reasonable possibility that the event may have been caused by other protocol-required therapies? Relatedness means that there are facts or reasons to support a relationship between other protocol-required therapies and the event.

The investigator must assess whether the adverse event is possibly related to any study mandated activity (including any screening procedure[s]). This relationship is indicated by a "yes" or "no" response to the question: "Is there a reasonable possibility that the event may have been caused by a study activity and/or procedure"?

The investigator is responsible for reviewing laboratory test results and determining whether an abnormal value in an individual study subject represents a clinically significant change from the subject's baseline values. In general, abnormal laboratory findings without clinical significance (based on the Investigator's judgment) are not to be recorded as adverse events. However, laboratory value changes that require treatment or adjustment in current therapy are considered adverse events. Where applicable,

clinical sequelae (not the laboratory abnormality) are to be recorded as the adverse event.

If an adverse event severity worsens from the date of onset to the date of resolution, record a single event for each level of severity on the Event eCRF.

The investigator is expected to follow reported adverse events until stabilization or reversibility.

9.2.2 Reporting Procedures for Serious Adverse Events

The investigator is responsible for ensuring that all serious adverse events observed by the investigator or reported by the subject that occur after signing of the informed consent through day 169/EOS visit, ET visit, or 30 days after the last dose of IP (whichever period is longer) are reported using the Events eCRF. All serious adverse events must be submitted to Amgen **immediately and no later than** 24 hours following the investigator's knowledge of the event via the Events eCRF.

If the electronic data capture (EDC) system is unavailable to the site staff to report the serious adverse event, the information is to be reported to Amgen via a paper Serious Adverse Event Contingency Report Form (also referred to as the electronic Serious Adverse Event [eSAE] Contingency Report Form) **immediately and no later than** 24 hours of the investigator's knowledge of the event. See Appendix B for a sample of the Serious Adverse Event Worksheet/eSAE Contingency Report Form. For EDC studies where the first notification of a Serious Adverse Event is reported to Amgen via the eSAE Contingency Report Form, the data must be entered into the EDC system when the system is again available.

The investigator must assess whether the serious adverse event is possibly related to the investigational product. This relationship is indicated by a "yes" or "no" response to the question: Is there a reasonable possibility that the event may have been caused by the investigational product? Relatedness means that there are facts or reasons to support a relationship between investigational product and the event.

The investigator must assess whether the adverse event is possibly related to other protocol-required therapies. This relationship is indicated by a "yes" or "no" response to the question: Is there a reasonable possibility that the event may have been caused by other protocol-required therapies? Relatedness means that there are facts or reasons to support a relationship between investigational product and the event.

The investigator must assess whether the adverse event is possibly related to any study mandated activity (including any screening procedure[s]). This relationship is indicated by a "yes" or "no" response to the question: "Is there a reasonable possibility that the event may have been caused by a study activity and/or procedure"?

The investigator is expected to follow reported serious adverse events until stabilization or reversibility.

Amgen will report serious adverse events and/or suspected unexpected serious adverse reactions as required to regulatory authorities, investigators/institutions, and IRBs/IECs in compliance with all reporting requirements according to local regulations and good clinical practice.

The investigator is to notify the appropriate IRB/IEC of serious adverse events occurring at the site and other adverse event reports received from Amgen, in accordance with local regulatory requirements and procedures.

